6.2 Exclusion Criteria

Participants are excluded from the study if any of the following criteria apply:

1. Is currently participating and receiving study therapy in a study of an investigational agent or has participated and received study therapy in a study of an investigational agent or has used an investigational device within 28 days of administration of MK-3475.

Note: Participants who have entered the follow-up phase of an investigational study may participate as long as it has been 4 weeks since the last dose of the previous investigational agent.

2. Has had chemotherapy, definitive radiation, or biological cancer therapy within 4 weeks (2 weeks for palliative radiation) prior to the first dose of study therapy, or has not recovered to CTCAE Grade 1 or better from any adverse events that were due to cancer therapeutics administered more than 4 weeks earlier (this includes participants with previous immunomodulatory therapy with residual immune-related adverse events). Participants receiving ongoing replacement hormone therapy for endocrine immune-related adverse events will not be excluded from participation in this study.
3. Has a history of a second malignancy, unless potentially curative treatment has been completed with no evidence of malignancy for 2 years.

Note: The time requirement does not apply to participants who underwent successful definitive resection of basal cell carcinoma of the skin, superficial bladder cancer or in situ cervical cancer, or other in-situ cancers.

4. Has clinically active CNS metastases and/or carcinomatous meningitis. Participants with previously treated brain or meningeal metastases may participate and be eligible for treatment provided they are stable and asymptomatic (without evidence of progression by MRI of the brain separated by at least 4 weeks after treatment), have no evidence of new or enlarging brain metastases, are evaluated within 4 weeks prior to first study treatment administration, and are off immunosuppressive doses of systemic steroids at least 2 weeks prior to enrollment.
5. Has a known hypersensitivity, intolerance or contraindication to any component of study treatment (eg, known deficiency of the enzyme DPD), including premedication.
6. Has any active infection requiring systemic therapy.
7. Has a history of (non-infectious) pneumonitis that required steroids or has current pneumonitis.
8. Has received prior therapy with compounds targeting PD-1, PD-L1, PD-L2, or a MAPK pathway inhibitor (eg, BRAF, MEK, ERK inhibitors).
9. Has an autoimmune disease that has required systemic treatment in the past 2 years with use of disease modifying agents, corticosteroids, or immunosuppressive drugs. Replacement therapy (eg, thyroxine, insulin, physiologic corticosteroid replacement therapy for adrenal or pituitary insufficiency) is not considered a form of systemic treatment.
10. Has a diagnosis of immunodeficiency or is receiving systemic steroid therapy or any other form of immunosuppressive therapy within 7 days prior to randomization.
11. Has known history of HIV infection. No HIV testing is required unless mandated by local health authority.

12. Has a known history of Hepatitis B (defined as HBsAg reactive) or known active Hepatitis C virus (defined as HCV RNA [qualitative] is detected) infection.

Note: No testing for Hepatitis B and Hepatitis C is required unless mandated by local health authority.

13. Has received live vaccine within 30 days of the planned start of study therapy.

Note: Seasonal influenza vaccines for injection are generally inactivated flu vaccines and are allowed; however intranasal influenza vaccines (eg, Flu-Mist[®]) are live attenuated vaccines, and are not allowed.

14. Has undergone major surgery and has not recovered adequately from any toxicity and/or complications from the intervention prior to starting study therapy.

15. Has baseline peripheral neuropathy/paresthesia

- a. Grade >1 for potential participants for Cohort A, D or E in Part 1
- b. Grade >0 for potential participants for Cohort B or C in Part 1 (oxaliplatin containing cohorts)
- c. Grade >2 for potential participants for Cohort A, D or E in Part 2
- d. Grade >1 for potential participants for Cohort B or C in Part 2 (oxaliplatin containing cohorts)

16. Have any medical, psychiatric, cognitive, or other conditions that may compromise the participant's ability to understand the participant information, give informed consent, comply with the study protocol, or complete the study.

17. Has symptomatic CHF (i.e. Grade 2 or higher), history or current evidence of clinically significant cardiac arrhythmia and/or conduction abnormality \leq 6 months prior to start of study treatment, except atrial fibrillation and PSVT.

18. Have a history of acute or chronic pancreatitis.

19. Have existing uncontrolled arterial hypertension (SBP \geq 150 mm Hg or DBP \geq 100 mm Hg) despite appropriate medical therapy.

20. Have a history of thromboembolic or cerebrovascular events within 6 months prior to registration, including TIAs, CVAs, deep vein thrombosis, or pulmonary embolism.

21. Have neuromuscular disorders associated with an elevated creatine kinase (eg, inflammatory myopathies, muscular dystrophy, amyotrophic lateral sclerosis, spinal muscular atrophy).

Potential Participants for Cohorts A, C or E who are to Receive Binimetinib:

22. Have a history of, or current, RVO or current risk factors for RVO (eg, uncontrolled glaucoma, ocular hypertension, history of hyperviscosity, or hypercoagulability syndromes).

23. Have retinal degenerative disease.

Potential Participants for Cohorts A, C, D or E:

24. Have a known history of Gilbert's Syndrome.

Potential Participants for Cohorts D or E:

25. Has a previous treatment with irinotecan will be excluded.
26. Has plans to use, or is using, any herbal medications/supplements or any medications or foods that are strong inhibitors or inducers of cytochrome P450 3A 4/5 ≤ 1 week prior to the start of study treatment.

Pregnancy Exclusion

27. A WOCBP who has a positive urine pregnancy test within 24 hours before the first dose of study treatment (see Appendix 6). If the urine test cannot be confirmed as negative, a serum pregnancy test is required. In such cases, the participant must be excluded from participation if the serum pregnancy result is positive.

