Despite recent advances, the intent of treatment for most of mCRC participants is palliative with few patients achieving long-term survival (5-year survival rate of 13.5%) [Centers for Disease Control and Prevention 2015]. Current SOC treatments for mCRC in the early-line setting include chemotherapy based on fluoropyrimidine, oxaliplatin, and irinotecan used in combination or sequentially, with option for monoclonal antibodies targeting VEGF (eg, bevacizumab, ziv-aflibercept) or its receptors (eg, ramucirumab) and in patients with Ras wild-type tumors, monoclonal antibodies targeting the EGF receptor (eg, cetuximab, panitumumab). Although the ORR reported in early line studies ranged from 31% to 60%, the DOR was limited (7.1 - 10.4 months) [Comella, P., et al 2009] [Diaz-Rubio, E., et al 2007] [Ducreux, M., et al 2011] [Porschen, R., et al 2007] [National Comprehensive Cancer Network 2015] [Colucci, G., et al 2005] [Tournigand, C., et al 2004] [Douillard, J. Y., et al 2010] [Hurwitz, H., et al 2004] [Van Cutsem, E., et al 2015] [Heinemann, V., et al 2014]. Ultimately, nearly all patients will require salvage therapies which have limited clinical benefit coupled with high toxicity. The ORR in the 2L setting for combination regimens (fluoropyrimidine plus oxaliplatin or irinotecan +/- anti-VEGF or anti-EGFR) is less than 23% while durations of benefit are limited (median PFS \leq 7 months) [Van Cutsem, E., et al 2012] [Bennouna, J., et al 2013] [Tabernero, J., et al 2015] [Giantonio, B. J., et al 2007] [Iwamoto, S., et al 2015] [Masi, G., et al 2015] [Rothenberg, M. L., et al 2008].

Treatment options for heavily pre-treated patients beyond the 2L setting are limited and associated toxicities can be severe. Although regorafenib and TAS-102 are the 2 commonly accepted SOC therapies for patients who have been treated with fluoropyrimidine-, irinotecan-, oxaliplatin-containing chemotherapies, anti-VEGF and an anti-EGFR agent (if KRAS wild-type) offer minimal benefits as ORR is \leq 2% for both agents [Grothey, A., et al 2013] [U.S. Prescribing Information 2012]. Minimal durability of clinical benefit is evidenced by a 6-month PFS rate of \sim 15%. Clearly, there is a high unmet medical need in developing novel combination regimens to improve the clinical outcome for patients with mCRC.

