9. Must have been previously treated with fluoropyrimidine, irinotecan, and oxaliplatin.

Note: Adjuvant chemotherapy counts as a first line of prior systemic therapy if there is documented disease progression within 12 months of chemotherapy completion.

Participants for Cohorts B and C

10. Must not have received prior systemic chemotherapy for Stage IV CRC.

Note: Participants who have received adjuvant chemotherapy for non-Stage IV CRC and have documented disease progression within 12 months of chemotherapy completion will not be eligible as these participants may have relative resistance to the proposed 1L regimen, which may undermine the adequate efficacy assessment of this 1L combination.

Participants for Cohorts D and E

11. Must have been previously treated with 1 line of therapy including a fluoropyrimidine plus an oxaliplatin-based regimen.

Note: Adjuvant chemotherapy counts as 1 line of prior systemic therapy if there is documented disease progression within 12 months of chemotherapy completion.

Participants for Cohorts A, C, and E

12. Participants must have a 12-lead ECG and ECHO or MUGA scan performed by the investigator or other qualified person to evaluate cardiac function prior to enrollment in the study. Adequate cardiac function will be assessed by:

- a) LVEF $\geq 50\%$ as determined by MUGA scan or ECHO; and
- b) QT interval calculated according to the Fridericia method (QTcF) value ≤ 480 msec (mean of 3 measurements corrected for heart rate using Fridericia's formula).

Contraception

Male participants:

13. A male participant must agree to use a contraception as detailed in Appendix 5 of this protocol during the treatment period and for at least 180 days, after the last dose of study treatment and refrain from donating sperm during this period.

- a) Male participants with pregnant partners must agree to use a condom.
- b) No additional method of contraception is required for the pregnant partner.

Female participants:

14. A female participant is eligible to participate if she is not pregnant (see Appendix 6), not breastfeeding, and at least one of the following conditions applies:

- a) Not a woman of childbearing potential (WOCBP) as defined in Appendix 6 OR
- b) A WOCBP who agrees to follow the contraceptive guidance in Appendix 6 during the treatment period and for at least 180 days after the last dose of study treatment.

Informed Consent

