7.7 Concomitant Therapy

If a participant does not discontinue all prior medications within 14 days of the first dose of study treatment, he/she may be included in the study if the investigator can rationalize that the specific use of a prior medication is not clinically relevant within the context of the trial.

Concurrent use of any prescription or non-prescription medication, or concurrent vaccination, during the course of the trial (ie, after randomization or treatment allocation) must first be discussed between the investigator and Sponsor prior to administration, unless appropriate medical care necessitates that therapy or vaccination should begin before the investigator and Sponsor can consult. The participant will be allowed to continue in the trial if both the Sponsor and the investigator agree.

Listed below are specific restrictions for concomitant therapy during the course of the trial: Participants are prohibited from receiving the following therapies during the Screening and Treatment Phases (including retreatment for post- CR relapse) of this trial: Participants who, in the assessment of the investigator, require the use of any of the treatments mention for

clinical management should be discontinued from treatment. Participants may receive other medications that the investigator deems to be medically necessary.

- Antineoplastic systemic chemotherapy or biological therapy not specified in this study
- Immunotherapy not specified in this protocol
- Chemotherapy not specified in this protocol
- Investigational agents other than pembrolizumab and binimetinib
- Radiation therapy

Note: Radiation therapy to a symptomatic solitary lesion or to the brain may be allowed at the investigator's discretion.

- Live vaccines within 30 days prior to the first dose of trial treatment and while participating in the trial. Examples of live vaccines include, but are not limited to, the following: measles, mumps, rubella, varicella/zoster, yellow fever, rabies, BCG, and typhoid vaccine. Seasonal influenza vaccines for injection are generally killed virus vaccines and are allowed; however, intranasal influenza vaccines (eg, FluMist®) are live attenuated vaccines and are not allowed.
- Systemic glucocorticoids for any purpose other than to modulate symptoms from an ECI that is suspected to have an immunologic etiology. The use of physiologic doses of corticosteroids may be approved after consultation with the Sponsor.

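### Exclusion 2 requires no toxicity recovery from palliative radiation or unlisted anticancer agents given in the last 4 weeks, so residual toxicity can enter the DLT window

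*Combined protocol and SAP*

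**What the plan says.** Section 6.2, criterion 2 has two limbs. The washout limb excludes anyone who "Has had chemotherapy, definitive radiation, or biological cancer therapy within 4 weeks (2 weeks for palliative radiation") before the first dose. The recovery limb excludes anyone who "has not recovered to CTCAE Grade 1 or better from any adverse events that were due to cancer therapeutics administered more than 4 weeks earlier".

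Section 6.1, criterion 9 sets the entry condition for Cohort A: "Must have been previously treated with fluoropyrimidine, irinotecan, and oxaliplatin". It does not cap the number of prior lines. The Introduction (Section 3) describes that population: "Although regorafenib and TAS-102 are the 2 commonly accepted SOC therapies for patients who have been treated with fluoropyrimidine-, irinotecan-, oxaliplatin-containing chemotherapies". It adds that toxicities beyond second line can be severe.

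Section 7.7 lists therapies prohibited during the Screening and Treatment Phases. The list opens with "Antineoplastic systemic chemotherapy or biological therapy not specified in this study" and goes on to immunotherapy, chemotherapy, other investigational agents and radiation. It leaves the investigator discretion to allow radiation to a symptomatic solitary lesion or to the brain. The same section has a general rule on earlier medicines: "If a participant does not discontinue all prior medications within 14 days of the first dose of study treatment", inclusion is still possible if the investigator can justify the use as not clinically relevant.

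**The concern.** The recovery limb makes sense only if everything given in the last 4 weeks has already been removed by the washout limb. That is not so. The washout limb itself lets palliative radiation in from 2 weeks, and it lists drug classes without naming targeted small-molecule agents. For such therapy the criterion, followed exactly, does not ask whether toxicity has resolved.

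The primary endpoint is the incidence of DLTs, and the recommended dose comes from very small groups. An adverse event carried over from recent therapy, and judged possibly related to the study drugs, would be charged to the combination. The point matters most in Cohort A, the most heavily pretreated group. Elsewhere, in the 28-day windows of Cohorts B to E, it concerns mainly palliative radiation.

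**Working it through.** **1. The two limbs of criterion 2 side by side**

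| Therapy before first dose | Washout limb | Recovery limb |
|---|---|---|
| Listed drug class or definitive radiation, within 4 weeks | Excluded | Not needed |
| Palliative radiation, within 2 weeks | Excluded | Not needed |
| Palliative radiation, 2 to 4 weeks earlier | Allowed | Does not apply |
| Anticancer agent of an unlisted class, within 4 weeks | Not reached | Does not apply |
| Any cancer therapeutic, more than 4 weeks earlier | Allowed | Grade 1 or better required |

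Rows three and four are the gap. Row three follows from the criterion's own words and needs no view about any drug.

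**2. Do other rules close it?**

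- The 14-day rule in Section 7.7 can be waived. It concerns prior medications, and Section 9.1.5.1 records treatment of the study disease separately from prior medications, so it may not reach anticancer drugs.
- The prohibited list in Section 7.7 covers radiation during Screening, subject to the discretionary exception. It does not name targeted agents and requires no recovery.
- Exclusion 1 covers investigational agents only. Exclusion 8 bars MAPK pathway inhibitors and does not mention regorafenib.
- The organ-function limits, the hypertension rule and the neuropathy limits in criterion 15 each catch particular toxicities only.
- Section 5.1.4 does not make a participant non-evaluable because of carried-over toxicity.

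**3. Can residual toxicity become a DLT?** Section 5.1.3 counts events assessed as possibly, probably or definitely related and removes those clearly unrelated. Most criteria need Grade 3 or higher, so a residual Grade 2 event is not itself a DLT. It could become one by worsening. It could also count through criteria 8 and 9 (discontinuation, or more than 25% of binimetinib doses missed), which have no grade threshold but still require attribution to study treatment.

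**4. What one event does.** From the protocol: target DLT rate 30%, minimum 3 participants per level, cap of 14. Table 2 is redacted, so I assume a standard mTPI: Beta(1,1) prior, target interval 0.25 to 0.35, and exclusion of a dose when P(p > 0.30) exceeds 0.95. A half-width of 0.03 gives the same decisions at n = 3, 6 and 14. As a check, 4 DLTs in 6 gives P(p > 0.30) = 0.971, which agrees with the Section 5.1.1.1 example that calls 4 of 6 unacceptably toxic.

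The decision goes to the interval with the largest posterior probability divided by its length. With F the posterior distribution function:

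- 0/3, F(p) = 1 − (1 − p)^4: below 0.6836/0.25 = 2.73; within (0.8215 − 0.6836)/0.10 = 1.38; above 0.1785/0.65 = 0.27. Escalate.
- 1/3, F(p) = 6p² − 8p³ + 3p⁴: below 0.2617/0.25 = 1.05; within (0.4370 − 0.2617)/0.10 = 1.75; above 0.5630/0.65 = 0.87. Stay.
- 2/3, F(p) = 4p³ − 3p⁴: below 0.0508/0.25 = 0.20; within (0.1265 − 0.0508)/0.10 = 0.76; above 0.8735/0.65 = 1.34. De-escalate.

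So one carried-over event turns 0/3 (escalate) into 1/3 (stay). Lowering the dose takes a second DLT. In larger groups a single event matters less: at n = 6 both 0 and 1 DLT give escalate, and at n = 14 so do 0, 1 and 2.

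**5. Illustration.** Assume a true DLT rate p = 0.20 and an independent carry-over DLT probability c, averaged over participants. The documents give no value for c. The observed rate is q = 1 − (1 − p)(1 − c).

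| c | q | Not escalating at n = 3: 1 − (1 − q)³ | De-escalate or exclude at n = 3: 3q²(1 − q) + q³ | De-escalate or exclude at n = 14: P(X ≥ 7) |
|---|---|---|---|---|
| 0 | 0.20 | 1 − 0.512 = 0.488 | 0.104 | 0.012 |
| 0.05 | 0.24 | 1 − 0.439 = 0.561 | 0.145 | 0.031 |
| 0.10 | 0.28 | 1 − 0.373 = 0.627 | 0.191 | 0.067 |

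**The case against.** The strongest reply is that the safeguards together leave little room. Section 7.7 starts from stopping prior medications, and an investigator would struggle to call a recent anticancer drug clinically irrelevant. Section 5.1.3 removes clearly unrelated toxicity, and Appendix 5 tells the investigator to weigh other drugs as the cause. Abnormal findings at the screening examination are recorded as medical history. Dose levels can grow to 14 participants, and the totality of the data decides the dose. All of this stands and keeps the likely effect small. None of it requires recovery from recent therapy, and attribution is hardest when another toxic treatment has only just ended.

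A reader might go further in four ways that the documents do not support:

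- **That regorafenib certainly escapes the washout.** The Introduction names it as standard therapy, but no section states its class, and whether exclusion 8 bars it cannot be settled from the text. If it is barred, that example falls away. The palliative-radiation gap remains.
- **That such agents have no washout at all.** The 14-day rule may apply, though it can be waived. The supported statement is that there is no fixed washout.
- **That one carried-over event lowers the dose.** Under the assumed settings it holds the dose.
- **That the response rate is contaminated too.** The Introduction puts ORR at 2% or less for regorafenib and TAS-102, and response is first assessed at 9 weeks with confirmation at least 4 weeks later.

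**Conclusion.** The point holds as a defect in the eligibility wording. Criterion 2 is inconsistent with itself, because it admits palliative radiation from 2 weeks but asks for recovery only from therapy older than 4 weeks. Neither its washout nor the Section 7.7 list names targeted small-molecule agents, although the Introduction describes a population that receives therapy beyond the three required drugs.

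The size is one possible misattributed event in a group of as few as 3. That is enough to turn escalate into stay, given the assumed mTPI settings. The probabilities in the working also rest on assumed true and carry-over DLT rates. The documents do not say how many participants enter within 4 weeks of such therapy or with unresolved toxicity, so no overall effect can be estimated. No calculation stated in the plan is wrong. This is an inexpensive improvement that protects the primary endpoint where the samples are smallest.

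**What to change.** In Section 6.2, criterion 2, delete the restriction to therapeutics given more than 4 weeks earlier. The recovery limb would then exclude anyone not recovered to CTCAE Grade 1 or better from adverse events due to any previously administered cancer therapy. This keeps the plan's own standard and its existing allowance for hormone replacement.

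Reconcile the therapy classes in criterion 2, criterion 8 and Section 7.7 with the Introduction, so that every prior anticancer class is covered somewhere. State whether regorafenib falls under criterion 8. The sponsor should set any washout interval for classes not now listed, because the documents give no basis for choosing one. Also state how the recovery limb relates to criterion 15, which sets separate grade limits for neuropathy.

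For participants already treated under the present wording, list the type and date of last anticancer therapy beside each DLT. Section 9.1.5.2 already has prior anticancer treatments reviewed.

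The cost is a few phrases in Sections 6.2 and 7.7 and one listing. A few candidates, mainly for Cohort A, would start later or be excluded.

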6.3 Lifestyle Restrictions

Participants receiving 5-FU (mFOLFOX7 or FOLFIRI) must avoid exposure to sunlight due drug-induced photosensitivity.

6.3.1 Meals and Dietary Restrictions

Participants should maintain a normal diet unless modification is required to manage AEs such as diarrhea, nausea, or vomiting.

6.3.2 Caffeine, Alcohol, and Tobacco

There are no study specific restrictions regarding caffeine, alcohol, and tobacco.

